1.3.5 Chronological sequence

Eligible patients having signed the consent form participate in the one-month run-in phase after which they were randomised conditional to the absence of hyperkalaemia ≥ 5.5 mmol/l on two occasions or on the day of randomisation or of serious adverse events.

The included and randomised patients participate in the study for a duration of 2 years on average, the latter of which can be amended by the Steering Committee in light of the rate of event occurrences. The study was completed when the number of incidents necessary for attaining a sufficient power has been observed. Blinding was lifted only in the case of a serious adverse event in which care management may be modified according to the treatment received by the patient: spironolactone/placebo; patients were followed until the end of the study.

Figure 1: Scheme of the study

Figure 1: ALCHEMIST trial design

(*): dosage of 25 mg/eod; patients presenting blood potassium > 5.5 mmol/l on two occasions will be excluded before randomization;
 (**): maximum dosage of 25 mg/d; could be reduced or temporarily suspended if blood potassium is > 5.5 mmol/l;
 From V1 to V12: Other visits will be scheduled if blood potassium is > 5.5 mmol/l.

Summary table of visits.

	Visit 1 W-4	Visit 2 W-2	Visit 3 D0	Visit 4 W+2	Visit 5 W+4	Visit 6 à 13 M3 to M24
Verification of the selection criteria	x					
Verification of the inclusion/exclusion criteria						
Pregnancy test (if applicable)	x					
Information/Informed consent	x					
Physical examination	x	x	x	x	x	x
ECG	x					
Dispensing of medication	x		x		x	x
Self-questionnaires on quality of life	x					x (**)
Randomisation			x			
Blood potassium	3/week	3/week	3/week	3/week	x	x
Verification of compliance		x	x	x	x	x
Dosage increase		x	x	x	x	x
Dosage adjustment (if necessary)				x	x	x
Concomitant treatments	x					x
SAEs		x	x	x	x	x

(**) only at V6, V9, V13, V17 and V21

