In none dialysed patients with heart failure, three international controlled trials showed a reduction in cardiovascular morbidity and mortality induced by aldosterone antagonists (spironolactone and eplerenone). Our group participated in the design, conducting and publication of these three studies. The beneficial effects of aldosterone antagonists involve cardiovascular remodelling, including collagen synthesis, as well as effects on endothelial and immune functions. A recent randomised controlled trial conducted in early-stage CKD showed that adding spironolactone to ACE-I or sartans reduces left ventricular mass and arterial stiffness, both of which are independent predictors of cardiovascular events in patients with ESRD. Most clinicians are reluctant to use aldosterone antagonists because of the risk of hyperkalaemia. However, recent studies have demonstrated the safety of spironolactone in anuric ESRD HD patients.

The primary objective is to determine the effects of Spironolactone versus Placebo on a combined endpoint of nonfatal myocardial infarction (MI) and acute coronary syndrome, hospitalization for heart failure, nonfatal stroke, or CV death.

The secondary objective, addressed by the present statistical analysis plan, is to estimate the effect of the treatment group (Spironolactone vs. Placebo) on the Quality of Life (SF-36; KD-QOL and Minnesota) of these patients with the dual pathology: CKD on hemodialysis and established cardiovascular pathology.

Data source(s):

- Data from the ALCHEMIST (Aldosterone antagonist Chronic HEModialysis Interventional Survival Trial) cohort.

2. Analysis objectives

The objective of the analysis is to estimate the effect of treatment group (Spironolactone vs. Placebo) on Quality of Life (QoL) measured by the SF-36 (generic questionnaire), the KD-QOL (kidney failure specific questionnaire) and the Minnesota Heart Failure (heart failure specific questionnaire) at various times during the trial (baseline, 3 months, 1 year, 2 years, 3 years and 4 years).

The analysis will be blinded to the treatment group attributed by randomization.

3. Analysis sample

A total of 750 randomized patients (375 per group) followed for an average of 4 years.

The analysis will be conducted on a intention-to-treat (ITT) and per-protocol (PP) basis, according to the populations defined in the statistical analysis plan of the primary objective (ITT and PP).

4. Study variables

a. Outcome

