The effect size, calculated as the mean difference between groups divided by its variance, will be assessed by the Cohen's D coefficient, and interpreted according to Cohen's recommendations.

The evolution curve of the score of each dimension of quality of life and their 95% confidence intervals according to treatment group at inclusion, 3 months, 1 year, 2 years, 3 years and 4 years will be represented using the SF-36 norms available in the French population by age and sex, and the deviations from the French mean and by treatment group will be shown. We will perform the test to the theoretical mean for each dimension and the 2 components.

d. Subgroup analysis

Subgroup analyses of each quality-of-life dimension (SF-36, KD-QOL and Minnesota) will be performed for the characteristics listed below:

Characteristic	Categories
Age (years)	≤ 75, >75 or ≤median, >median
Pre-existing diabetes at baseline	Yes, No
History of ASCVD	Yes, No
IMC (kg/m ²)	≤30, >30 or <23, 23-30, >30 or according to quantiles
History of HF hospitalisation	Yes, No
EF < 40%	Yes, No
Serum potassium at baseline	≤ 4.5, >4.5 or ≤median, >median
Use of potassium binder at baseline	Yes, No
Use of angiotensin-converting enzyme inhibitors (ACEi) or angiotensin receptor blocker (ARB) at baseline	Yes, No
Systolic blood pressure	≤ median, > median
Dialysis vintage	≤ median, > median
Haemodiafiltration	Yes, No

6. Principal analysis

The objective of the analysis is to estimate the effect of treatment group (Spironolactone vs. Placebo) on Quality of Life (SF-36, KD-QOL and Minnesota) measured at baseline, 3 months, 1 year, 2 years, 3 years and 4 years.

This leads us to take into account data repetition. We are in a case of analysis with repeated measurement (intra-subject correlation) and this leads us to use the **linear mixed model**.

A. Bivariate & Multivariate analysis

1. List of variables

→ Variables to be explained:

- ✓ SF-36 :
 - Physical Functioning [QT]
 - Role-Physical [QT]
 - Bodily Pain [QT]
 - Mental Health [QT]

- Role-Emotional [QT]
- Social Functioning [QT]
- Vitality [QT]
- General Health [QT]
- Physical Component Summary [QT]
- Mental Component Summary [QT]
- ✓ **KD-QOL :**
 - Burden of kidney disease [QT]
 - Symptoms/Problems [QT]
 - Effects of kidney disease on daily life [QT]
- ✓ **Minnesota :**
 - Physical [QT]
 - Mental [QT]
 - Social [QT]
 - Incapacity [QT]

➔ **Explanatory variables:**

- ✓ **Interest factor**

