 - Treatment group (Spironolactone vs Placebo) (blind coded variable) [QL]
- ✓ **Confounding factors**
 - Age [QT]
 - Sex [QL]
 - Smoking [QL]
 - BMI [QT]
 - Center [QL]
 - Pre-existing CV disease [QL]
 - Pre-existing diabetes at baseline [QL]
- ✓ **Event variables**
 - Date of baseline
 - Date of birth
 - Follow-up time
 - Date of death
 - Date of last follow-up
 - Date of non-fatal event:
 - Hospitalization for heart failure
 - Non-fatal myocardial infarction (MI)
 - Acute coronary syndrome
 - Non-fatal stroke

2. Model used

«Linear Mixed Model». *Proc Mixed from SAS.*

The linear mixed model procedure allows correlated data with non-constant variability to be taken into account. The linear mixed model therefore offers the flexibility to model not only the means of the data, but also their variances and covariances. It also allows time-dependent explanatory variables (such as intercurrent events) to be taken into account. When recurrent events are recorded along follow up, they will be accounted for with repeated time-dependant covariate.

The model will be run on the complete data for each dimension of quality of life, after imputation following the imputation rules indicated by the developers of each questionnaire where applicable. Given missing data, which may vary from one dimension to another, even after imputation, the numbers may vary from one dimension to another.

a. Bivariate & Multivariate model: «Linear Mixed Model»

Application conditions

- Assumptions:
 - ❖ The dependent variable is considered to be linearly related to the fixed factor.
 - ❖ Fixed effects create an estimate of the mean of the dependent variable.
 - ❖ The dependent variable is also assumed to have a normal distribution.

Note: in the event of non-normality of a quality-of-life score, we will run a generalized model instead.

Model fit quality

- A linear mixed model is one that includes both fixed and random effects.
- Fixed effects describe the relationships between the covariates and the dependent variable for an entire population.
- Random effects are sample-specific.
- The linear mixed model is written as follows:
$$Y = \beta X + \gamma Z + \epsilon$$
- Fitting a linear mixed model enables us to estimate the mean of the coefficients β the vector of fixed-effect parameters and γ of the random effects parameter vector.

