- By fitting a linear mixed model, we can also estimate the standard deviation of these coefficients across groups, as well as the standard deviation of individual observations from group means.

Parameter estimates will be reported with their probabilities.

Statistical tests will be two-sided, with $\alpha = 0.05$ as the significance threshold. Each quality-of-life dimension of each questionnaire will be analyzed at this threshold, without correction for multiple testing, in line with standard practice in this field. In fact, the questionnaires are constructed in a paradigm of mutually independent dimensions.

For subjects with QoL data available after an intercurrent event, these events will be treated as time-dependent covariates.

In practice, we will carry out:

On the one hand, for each dimension of quality of life (SF-36, KD-QOL and Minnesota):

- *A model for each quality of life dimension (SF-36, KD-QOL and Minnesota) with a treatment group variable.*
- *A model for each quality of life dimension (SF-36, KD-QOL and Minnesota) with interaction between treatment group and measurement time.*
- *A model for each quality of life dimension (SF-36, KD-QOL and Minnesota) with treatment group variable and confounders.*
- *A model for each quality of life dimension (SF-36, KD-QOL and Minnesota) with treatment group-measurement time interaction and confounding factors.*
- *A model for each quality of life dimension (SF-36, KD-QOL and Minnesota) with treatment group variable, confounders, time-dependent variables and search for treatment group-factor interaction.*
- *A model for each QoL dimension (SF-36, KD-QOL and Minnesota) with treatment group variable, subgroup variables and treatment group-subgroup variable interaction.*

*On the other hand, if a dimension of quality of life (SF-36, KD-QOL and Minnesota) is non-normal, a **transformation by a Log function** will be performed.*

7. Sensitivity analysis

Sensitivity analysis will be performed for each dimension of quality of life, on complete and incomplete data even after imputation rules indicated by the developers of each questionnaire where applicable.

8. Latent Class Trajectory Model : « Group-Based Trajectory Modeling – GBTM »

- Trajectory profile for each dimension of Quality of Life (SF-36, KD-QOL and Minnesota) measured at baseline, 3 months, 1 year, 2 years, 3 years and 4 years.

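### Quality-of-life SAP: the treatment-only mixed models count the pre-treatment score as an outcome, so they dilute the effect, and none of the six listed models or their contrasts is named as principal

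*SAP*

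**What the plan says.** All references are to the QoL SAP unless the main SAP is named.

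- **Outcome.** Section 6 makes QoL a repeated outcome, "measured at baseline, 3 months, 1 year, 2 years, 3 years and 4 years". The visit table in main SAP section 1.3.5 puts the first questionnaire at Visit 1, four weeks before randomisation, and the later ones "only at V6, V9, V13, V17 and V21".
- **Covariates.** Section 6.A.1 lists age, sex, smoking, BMI, centre, prior cardiovascular disease and diabetes. The baseline QoL score is not listed.
- **Models.** Section 6.A.2 lists six per dimension. The first is "A model for each quality of life dimension (SF-36, KD-QOL and Minnesota) with a treatment group variable" and the third adds confounders. The second and fourth are the versions "with interaction between treatment group and measurement time". The fifth adds time-dependent variables and the sixth adds subgroup interactions. None is named as principal and no contrast is stated.
- **Events.** A sentence before the list says: "For subjects with QoL data available after an intercurrent event, these events will be treated as time-dependent covariates". The events are heart-failure hospitalisation, MI, acute coronary syndrome and stroke.
- **Data used.** "The model will be run on the complete data for each dimension of quality of life", after the questionnaire developers' imputation rules. Section 7 plans a sensitivity analysis on complete and incomplete data.
- **Follow-up.** Section 3: "A total of 750 randomized patients (375 per group) followed for an average of 4 years". Main SAP sections 1.3.1, 1.3.4 and 1.3.5 give 2 years on average.

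**The concern.** At Visit 1 nobody has been randomised, so the expected group difference is zero whatever the drug does. A model with one treatment coefficient over all times gives that zero a share of the weight and pulls a real effect towards nothing. It also gives up the precision that the baseline score would provide as a covariate.

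The listed events are components of the primary endpoint, which the drug is meant to reduce. Adjusting for them removes any benefit that reaches QoL by preventing them.

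With 17 dimensions, six models each and no named contrast, a reader cannot tell in advance which number is the trial's QoL result. The diluted, undiluted and event-adjusted versions estimate different quantities.

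**Working it through.** **Inputs from the documents.** Six outcome times (baseline plus five). Spacing check: V6 to V13 cover M3 to M24 in eight visits, so they are 3 months apart. V6, V9 and V13 are then 3, 12 and 24 months, and at the same spacing V17 and V21 are 36 and 48 months. 375 patients per arm; QoL difference of interest 5 points (section 5c); annual event probabilities 0.18 and 0.126 (main SAP 1.3.4).

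**The plan's own figure.** The only sample-size figure is 750, set for the primary endpoint. The rates −ln(0.82) = 0.1985 and −ln(0.874) = 0.1347 give a hazard ratio of 0.679. Schoenfeld's formula then needs 209 events. Mean two-year event probability is (0.3276 + 0.2361)/2 = 0.282, and 209/0.282 gives about 742, close to 750 with no allowance for post-randomisation dropout. The plan states no QoL SD, correlation or power, so those below are assumptions.

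**Dilution, full attendance.** With free visit means, the single treatment coefficient is a weighted mean of the visit-specific differences, with weights w = V⁻¹1/(1′V⁻¹1). Under compound symmetry each of m times gets 1/m, whatever the SD or correlation.

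- Six times: 5 × 5/6 = 4.17.
- Four times (to 2 years): 5 × 3/4 = 3.75.

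Under AR(1) or spatial-power covariance with correlation 0.4 to 0.8, the baseline weight is 0.20 to 0.36 (six times) or 0.30 to 0.42 (four times). The expected estimate is then 5 × (1 − w), about 3.2 to 4.0 or 2.9 to 3.5.

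**Dilution, declining attendance (assumed).** Replace V⁻¹ by A, the average over patients of the inverse covariance of the visits each attended, with monotone dropout. Compound symmetry, correlation 0.5 to 0.7.

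| Attendance at the five follow-up visits | Baseline weight | Expected estimate of 5 |
|---|---|---|
| 90/80/50/25/8% | 0.33–0.34 | 3.29–3.35 |
| 90/75/45/15/3% | 0.35–0.36 | 3.19–3.25 |

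**Precision (assumed SD 23, correlation r).** At full attendance, as written, Var = (2/375) × 23² × (1 + 5r)/6. With equal baseline means, Var = (2/375) × 23² × [(1 + 4r)/5 − r²].

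- r = 0.5: SE 1.28 against 0.99.
- r = 0.7: SE 1.45 against 0.87.

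Under the two attendance patterns, the SEs are 1.37–1.51 against 1.02–1.21. Power for a true 3-point effect is 24–31% against 70–84%.

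**Models with treatment-by-time.** Each visit has its own difference, so the post-baseline contrasts carry no baseline zero. The second and fourth models, and the tests at each time point in section 5c, are not diluted.

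**Event adjustment.** By 2 years the event probabilities differ by 0.3276 − 0.2361 = 0.0915. If an event costs 10 points (assumed), about 0.9 points of benefit act through events. A simulation of 200,000 patients with the plan's rates and an assumed 3-point direct effect gave 3.55–3.81 from the treatment-by-time model, falling to 2.85–3.09 with event adjustment. The planned rates include cardiovascular death, after which there is no questionnaire, so the loss through non-fatal events alone would be smaller.

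**The case against.** Several stronger readings are tempting, and the text does not support them.

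- *All the principal models are diluted.* They are not. The second and fourth carry treatment-by-time, and keeping baseline in the outcome vector is then acceptable.
- *A true 5-point benefit would be reported as falling short of the plan's threshold.* The threshold stands in section 5c beside the visit-by-visit tests, which are undiluted. Only the pooled coefficients shrink.
- *The main analysis is restricted to completers.* This is not established. The sentence concerns each dimension after item imputation and says numbers may vary between dimensions, which fits computable scores. Elsewhere the plan states completeness over time explicitly. On the other side, section 7 contrasts complete with incomplete data after imputation, and an uncomputable score cannot be modelled. The wording is ambiguous. The completer reading also cannot be combined with the 3.2–3.4 figure, which needs patients with missing visits in the model. With completers only, the figure is 4.17.
- *Every model conditions on events.* Only the fifth names time-dependent variables. The general sentence may reach further, but does not say so.
- *The 4-year follow-up statement is simply wrong.* The main SAP schedules questionnaires beyond M24 and lets the Steering Committee amend the duration. The documents disagree, but do not show which average is right.

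It is also fair that the dilution runs towards zero and creates no false benefit, that the power figures rest on assumptions, and that main SAP section 1.2 places QoL among hypothesis-generating objectives.

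The central point stands: the treatment-only models are diluted, and nothing says they are not the answer.

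**Conclusion.** The concern holds for the first and third models as written. The fifth and sixth also name no treatment-by-time term. The loss is one sixth of a constant effect with six attended times and one quarter with four, under compound symmetry. It is larger under serial correlation or attrition, with the size resting on the assumed covariance and attendance. All of this takes the effect as constant after baseline.

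The fifth model does not estimate the total treatment effect. What the complete-data rule means, and how far the event sentence reaches, are open questions rather than shown errors.

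This should be fixed, but it is not critical: QoL lies outside the hierarchical test, and the primary result is untouched.

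**What to change.** Before unblinding, amend section 6.A.2 of the QoL SAP to:

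1. Name one principal model per dimension: post-baseline scores as outcome, with baseline score, treatment, visit, treatment-by-visit and centre. Alternatively, keep baseline in the outcome vector with its group means constrained equal, so that patients without a baseline questionnaire stay in.
2. State the contrast, for example the difference at one named visit or the average over named visits.
3. Say that every available questionnaire enters, and define the complete-data wording.
4. Label the treatment-only, event-adjusted and any completer models as supportive or exploratory, and limit the intercurrent-event sentence to the models it is meant for.

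Separately, reconcile the 4-year average in section 3 of the QoL SAP with the 2-year average in the main SAP.

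The cost is SAP wording and some programming. All the data needed are already in the questionnaire schedule.

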Note: all patients with a missing Quality of Life (SF-36, KD-QOL and Minnesota) dimension at all follow-up times will be excluded from the latent class analysis.

a. Identification of Latent Class Trajectories

The various Latent Class Trajectories of each dimension of Quality of Life (SF-36, KD-QOL and Minnesota) are defined using Latent Class Trajectory Models, enabling us to obtain a variable in k trajectories from measured at baseline, 3 months, 1 year, 2 years, 3 years and 4 years.

1. Preliminary description and application conditions

- Measurement time metrics

The time measurement will be indicated transparently and described briefly.

Subjects with complete follow-up will be compared with those with incomplete on relevant characteristics. Significant variables be added as covariates in the Latent Class Trajectory Model.

2. Latent Class Trajectory Model

- These trajectories will be modeled:
 - With SAS, using Proc TRAJ (7), with the following parameters distribution ZIP (Zero Inflated Poisson) for modeling discrete quantitative variables.
- Model comparison and selection of the number of latent classes
 - Using Proc TRAJ in SAS:
 - Best model
Present the evolutionary graph by class of the absolute absolute BIC (Bayesian Information Criterion) values of the Linear, Quadratic and Cubic models.

Note: the best model is the curve model which lies above all the rest.
 - Selecting the number of latent classes
The BIC (Bayesian Information Criterion) is the most suitable selection criterion.
 - The minimum number of patients in each trajectory should be at least 5% of the sample (8).

3. Qualitative characterization and labeling of trajectory classes: description of characteristics at baseline

- Identified trajectories will be described using a graphical representation of the graphical representation of the means (with 95% CI) of the different trajectory classes of the Kellgren stage over time (9) (=> Graph 1, produced using the SAS macro %TRAJPLOTNEW

b. Explanatory factors

✚ **Interest factor**

- ❖ Treatment group (Spironolactone vs Placebo) (blind coded variable) [QL]

✚ **Confounding factors**

- ❖ Age [QT]
- ❖ Sex [QL]
- ❖ Smoking [QL]
- ❖ BMI [QT]
- ❖ Center [QL]
- ❖ Pre-existing CV disease [QL]
- ❖ Pre-existing diabetes at baseline [QL]

c. Factors associated with profiles of each dimension of Quality of Life (SF-36, KD-QOL and Minnesota)

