Bivariate & Multivariate analyses will be used to identify factors associated with profiles of each dimension of Quality of Life (SF-36, KD-QOL and Minnesota).

✚ If K classes =2: binary logistic regressions

✚ If K classes >2: there are several possibilities, depending on the trajectories identified and the objective sought:

- ❖ Several binary logistic regressions with the same reference modality of trajectories
- ❖ Ordinal logistic regression if trajectory classes are ordered
- ❖ Bivariate & Multivariate multinomial logistic regression

The reference modality in these models is defined with the Methodologist and Clinician. If there is no preference, the reference modality will be the one with the largest number of employees.

1. List of variables

- **Variable to be explained:**
 - Profiles of each dimension of Quality of Life (SF-36, KD-QOL and Minnesota)
- **Explanatory factors**
 - **Interest factor**
 - Treatment group (Spironolactone vs Placebo) (blind coded variable) [QL]
 - **Confounding factors**
 - Age [QT]
 - Sex [QL]
 - Smoking [QL]
 - BMI [QT]

- Center [QL]
- Pre-existing CV disease [QL]
- Pre-existing diabetes at baseline [QL]

2. Model used

« Logistic regression model ». Proc logistic from SAS.

- **Bivariate & multivariate model: « Logistic regression model ».**

Application conditions

- Assumption of independence of observations.
- Assumption of logit linearity for quantitative variables.
 - Box-Tidwell test (addition of an interaction term $X \cdot \ln(X)$ in the model): the significance of the interaction indicates a deviation from linearity.
 - Graphical method:
Variable X divided into deciles

Calculation of the proportion $\pi(X)$ of events observed for each decile each decile.

- The graphical representation of $\ln\left(\frac{\pi(X)}{1-\pi(X)}\right)$ as a function of the deciles should have a linear form.

- Model adequacy tests (Pearson or deviance): a significant test may indicate a deviation from linearity.

If the hypothesis is not valid for a quantitative variable X, we can transform it (X^2 , X^3 , \sqrt{X} , $\ln(X)$,...) or discretize it into classes.

- **Model goodness of fit**

- Likelihood ratio test: a significant test indicates that the overall model is more informative than the null model.
- Hosmer-Lemeshow goodness-of-fit test: if the test is significant, the model does not fit the data.

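### The supplementary QoL trajectory analysis regresses a model-assigned class on treatment as if the class were observed, with no allowance for classification error

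*SAP*

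**What the plan says.** QoL SAP section 8.a fits latent class trajectories to each QoL dimension over six times (baseline, 3 months, then years 1 to 4) with Proc TRAJ, "enabling us to obtain a variable in k trajectories". Two rules govern how many classes are kept:

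- an information criterion, of which the plan writes "The BIC (Bayesian Information Criterion) is the most suitable selection criterion";
- a floor on class size, worded as "The minimum number of patients in each trajectory should be at least 5% of the sample".

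Section 8.c makes the class the dependent variable in Proc logistic and names treatment group as the factor of interest. The model depends on the number of classes: "If K classes =2: binary logistic regressions"; for more than two, the options include "Several binary logistic regressions with the same reference modality of trajectories", ordinal regression and multinomial regression.

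The listed model checks (logit linearity, likelihood ratio, Hosmer-Lemeshow, R², ROC curve, residuals) concern the fit of the logistic model to the class variable as given. Section 8 does not mention posterior probabilities, a rule for assigning patients to classes, a threshold for classification quality, weights or a correction. Hard assignment to one class is therefore inferred from the class being a Proc logistic outcome; it is not written down.

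Two provisions bear on incomplete data. Patients with a dimension missing at every follow-up time are excluded. Characteristics that differ between complete and incomplete follow-up are added as covariates to the trajectory model.

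**The concern.** A trajectory model gives each patient a probability of belonging to each class. Reducing that to one label and regressing the label on treatment replaces the outcome with an error-prone version of itself.

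Error is likely here. The exclusion rule removes only patients with no follow-up score, so a patient who dies or leaves before year 1 is still classified from two of the six measurements. The QoL SAP's own background (section 1) gives an unadjusted mortality of 29% at 2 years in this population, and section 9 rules out imputation beyond the questionnaire developers' rules. Short series should be common, and they determine the class weakly.

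What is at stake is the treatment odds ratio from section 8, which is planned for each of 17 dimensions (10 SF-36, 3 KD-QOL, 4 Minnesota). The likely harm is a diluted estimate read as no effect on QoL trajectory.

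**Working it through.** **Inputs.** From the plan: 375 per arm (QoL SAP section 3), two-sided 5% tests (section 6), six measurement times. The plan gives no number of classes, class shares, classification accuracy or effect for this analysis, so those are assumptions and there is no trajectory figure to reproduce. The 375 per arm comes from the main SAP's section 1.3.4. It can be recovered with a hazard ratio of ln(0.874)/ln(0.82) = 0.679. The Schoenfeld formula at 80% power then gives 209 events. With a mean 2-year event probability of 0.282, that is about 742 patients against the stated 750, before any dropout allowance.

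**Two classes, symmetric error e unrelated to treatment.** If the true class share is p, the observed share is q = e + (1 − 2e)p. The observed odds ratio uses q in place of p. Power comes from the Wald statistic, with SE = √[1/(375·q₁(1 − q₁)) + 1/(375·q₀(1 − q₀))].

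Worked case, 60% against 50%:

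- e = 0: OR = (0.60/0.40)/(0.50/0.50) = 1.50; ln OR = 0.405, SE = 0.148, z = 2.75, power 78%.
- e = 0.10: q₁ = 0.10 + 0.80 × 0.60 = 0.58, q₀ = 0.50; OR = 1.38; ln OR = 0.323, SE = 0.147, z = 2.20, power 59%.
- e = 0.20: q₁ = 0.20 + 0.60 × 0.60 = 0.56, q₀ = 0.50; OR = 1.27; ln OR = 0.241, SE = 0.147, z = 1.65, power 38%.

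The log odds ratio shrinks by 20% and 41%.

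| True shares | e = 0 | e = 0.10 | e = 0.20 |
|---|---|---|---|
| 60% vs 50% | OR 1.50, power 78% | 1.38, 59% | 1.27, 38% |
| 30% vs 20% | OR 1.71, power 88% | 1.47, 66% | 1.30, 41% |

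**Simulation of the two-step procedure.** Settings (all assumed): two-class Gaussian trajectory model fitted by EM, six visits, dropout from year 1 onward, 30% class share on placebo, 375 per arm, 300 runs per setting, assignment to the most likely class, then a log odds ratio with Wald interval. True OR 2.0:

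| Correctly assigned | Median OR | 95% CI coverage | Power | Mean model SE | Empirical SD |
|---|---|---|---|---|---|
| 87% | 1.67 | 76% | 87% | 0.155 | 0.165 |
| 73% | 1.38 | 40% | 49% | 0.170 | 0.165 |
| 65% | 1.26 | 26% | 26% | 0.178 | 0.175 |

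With the class known without error, the median OR was 2.01 to 2.04, coverage 94% to 97% and power above 99%. The model SE stays close to the empirical SD, so coverage is lost because the interval is centred in the wrong place. With a true OR of 1.0, the median was 1.00 to 1.02 and the rejection rate 3% to 6%.

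**Three classes.** Assume 80% of each class is correctly assigned. Classes 1 and 3 lose 20% to class 2, and class 2 loses 10% to each side. Take placebo shares 0.3/0.3/0.4 and spironolactone shares 0.2/0.2/0.6, so that class 1 against class 2 has a true OR of 1.00.

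- Placebo: class 1 = 0.24 + 0.03 = 0.27; class 2 = 0.06 + 0.24 + 0.08 = 0.38.
- Spironolactone: class 1 = 0.16 + 0.02 = 0.18; class 2 = 0.04 + 0.16 + 0.12 = 0.32.
- Observed OR = (0.18/0.32)/(0.27/0.38) = 0.79.

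A null contrast has moved away from 1 with no difference in error between arms. In four other three-class scenarios with the same error pattern, every non-null contrast moved towards 1 (for example 2.78 to 1.95).

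**The case against.** The strongest defence is that little depends on this analysis. QoL SAP section 6 names the linear mixed model as the principal analysis, and it estimates the treatment effect without any classes. The main SAP (section 1.2) lists QoL among the objectives for hypothesis generation. Section 8 looks for factors associated with trajectory profiles and feeds no primary or hierarchically tested result. All of this stands and limits the weight of the point.

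The plan also adjusts the trajectory model for characteristics linked to incomplete follow-up. That may improve classification of patients with short series, but it does not carry the remaining class uncertainty into the logistic model, and treatment is not named as a predictor of class.

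The figures rest on assumed error rates. Symmetric error is a convenience, and less plausible if a class holds only about 5% of patients. The exclusion rule leaves somewhat fewer than 375 per arm, so starting power is slightly overstated. This also stands: the figures are illustrations and not properties of the plan.

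Three stronger readings are tempting and not supported:

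- **The odds ratio always moves towards 1.** This is assured only for two classes with error unrelated to treatment; section 8.c allows more.
- **The intervals are far too narrow, or false positives are inflated.** Class uncertainty is indeed left out of the standard errors, but in the simulation these were about right and the test kept its level at a true OR of 1.0.
- **Error differs by arm here.** That would need follow-up to differ by arm, and the document gives no figure for it.

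**Conclusion.** The point holds for section 8 of the QoL SAP only. As written, the class is treated as an observed outcome, and the treatment odds ratio is biased when classes are imperfectly separated and treatment affects class membership.

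For two classes and error unrelated to treatment, the bias is towards 1: a log odds ratio smaller by about 20% at 10% error and 41% at 20% error in the 60% against 50% case, with power down from 78% to 59% and 38%. For more than two classes, or error that differs by arm, the direction of a single contrast cannot be stated in advance. Confidence intervals miss the true value mainly because the estimate is biased. A reader might infer that the trial's main QoL result is compromised; it is not, since the mixed model does not use the classes, and the primary endpoint is untouched.

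The size depends on assumed class shares and accuracy, and on assignment to a single class, which the plan implies without stating. The change is worth making but is not critical to the trial's conclusions.

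**What to change.** In section 8, replace the regression of assigned class on treatment with one of two methods:

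- estimate treatment and covariates as predictors of class probability within the trajectory likelihood; or
- use a bias-adjusted three-step method based on each patient's posterior probabilities.

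State the assignment rule. Report the mean posterior probability per class and by number of available visits. Keep the assigned class for graphs and description only.

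The cost is some extra programming and no new data. One small downside is that classes may shift slightly when predictors enter the trajectory model.
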